### 4) Allergies and Adverse Drug Reaction

- a) Hypersensitivity to abatacept or one of its excipients

### 5) Other Exclusion Criteria

- a) Subjects who are unable to complete study procedures
- b) Subjects with a history or suspicion of unreliability, poor cooperation, or non-compliance with medical treatment
- c) Prisoners or subjects who are involuntarily incarcerated. (Note: under certain specific circumstances a person who has been imprisoned may be included or permitted to continue as a subject. Strict conditions apply and Bristol-Myers Squibb approval is required.

- d) Subjects who are compulsorily detained for treatment of either a psychiatric or physical (eg, infectious disease) illness

**6) MRI Contraindications (for MRI sub-study only)**

For a subject who intends to participate in the MRI sub-study, the radiologist at the site's MRI facility is responsible for determining if a subject is contraindicated from having this procedure. If the subject is contraindicated, the subject must be dropped from the MRI sub-study. The following is a list of some common conditions that may preclude the subject from having MRI of the hands or wrists. However, this should not be used as a substitute for local clinical standards of care. The ultimate decision to perform an MRI on an individual subject in the MRI sub-study rests with the site radiologist, the investigator, and the standard set by the local Ethics Committee:

- a) Subjects who have a history of claustrophobia.
- b) Subjects who have a physical limitation related to fitting in the bore of the magnet (ie, body weight in excess of 250 pounds or 113.4 kilograms).
- c) Subjects with tattoos on the area to be imaged.
- d) Subjects who have a history of allergic reaction to contrast agents
- e) Subjects who had exposure to a radiological contrast agent within the 72 hours prior to the MRI examination.
- f) Subjects who have joint replacements in the leg that is being evaluated by the MRI examination.
- g) Subjects with a pacemaker, epicardial pacemaker wires, MRI-incompatible cardiac valve prostheses, MRI-incompatible vascular clips less than two-months old, or MRI-incompatible aneurysm clips of any age.
- h) Subjects with MRI-incompatible cochlear implants.
- i) Subjects with spinal nerve stimulators.
- j) Subjects with an infusion pump.
- k) Subjects with metallic fragments in the eyes/orbits or in the vicinity of the brain or major neurovascular structures of the body, subjects with an employment history which involves exposure to welding, or subjects who have shrapnel any place in their body.

Eligibility criteria for this study have been carefully considered to ensure the safety of the study subjects and that the results of the study can be used. It is imperative that subjects fully meet all eligibility criteria.

**3.3.3 Women of Childbearing Potential**

Women of childbearing potential (WOCBP) is defined as any female who has experienced menarche and who has not undergone surgical sterilization (hysterectomy or bilateral oophorectomy) and is not postmenopausal. Menopause is defined as 12 months of amenorrhea in a woman over age 45 years in the absence of other biological or physiological causes. In addition, females under the age of 55 years must have a serum follicle stimulating hormone, (FSH) level > 40 mIU/mL to confirm menopause.

\*Females treated with hormone replacement therapy, (HRT) are likely to have artificially suppressed FSH levels and may require a washout period in order to obtain a physiologic FSH level. The duration of the washout period is a function of the type of HRT used. The duration of the washout period below are suggested guidelines and the investigators should use their judgement in checking serum FSH levels.

- 1 week minimum for vaginal hormonal products (rings, creams, gels)
- 4 week minimum for transdermal products
- 8 week minimum for oral products

Other parenteral products may require washout periods as long as 6 months. If the serum FSH level is > 40 mIU/ml at any time during the washout period, the woman can be considered postmenopausal.

### **3.3.4 Screening for Malignancy**

It is recommended that all subjects should have been assessed for age and gender appropriate malignancy (e.g. breast cancer, gynecologic cancers, prostate cancer, and colon cancer) and any other malignancy for which an individual subject is at an increased risk at the investigator's discretion (e.g., lung cancer) prior to enrollment.

All subjects who were diagnosed with IIM in the past year must have been screened for occult malignancy at the discretion of the investigator.

Subjects who are anti-TIF1- $\gamma$  (p155/140) autoantibody positive and are more than 1 year from IIM diagnosis must also have undergone screening for occult malignancy in the last year at the discretion of the investigator.

Testing can include any of the following, at the discretion of the investigator:

- Chest imaging (chest CT required for subjects with a history of smoking, CXR acceptable for all other subjects)
- Abdominal imaging (CT or ultrasound)
- Laboratory testing: alpha-fetoprotein, CA-125
- Documented skin exam for malignancy
- Screening for gastrointestinal malignancy (e.g., stool analysis for occult blood, colonoscopy, sigmoidoscopy)
- Screening for breast cancer (e.g., imaging [mammography or MRI]) for female subjects over the age of 40
- Screening for cervical cancer (e.g., Pap test and human papillomavirus [HPV] testing) for all female subjects
- Screening for prostate cancer (e.g., digital rectal exam, Prostate Specific Antigen testing) for all male subjects over the age of 40

For prior testing results, a copy of the report must be obtained and reviewed by the investigator and placed in the subject binder.

In some cases, subjects who are determined by the investigator to be at low risk of malignancy may not require any of the above testing. All such cases may be discussed with the medical monitor.

[REDACTED]

[REDACTED]

[REDACTED]

[REDACTED]

[REDACTED]

[REDACTED]

[REDACTED]

[REDACTED]

[REDACTED]

[REDACTED]

[REDACTED]

[REDACTED]

[REDACTED]

[REDACTED]

[REDACTED]

[REDACTED]

[REDACTED]

[REDACTED]

### **3.5 Discontinuation of Subjects following any Treatment with Study Drug**

Subjects who discontinue treatment with investigational product during the Double-Blind Treatment Period (Day 1 - Week 24) must be assessed for all efficacy measures and for safety at the originally scheduled Week 24 (Day 169 from baseline) time-point (see Post-Study Drug Efficacy Visit - [Table 5.1-4](#)).

All subjects who discontinue study drug at any time throughout the study, require visits to assess safety and immunogenicity at Day 85 and Day 169 after the last dose of study drug (see [Table 5.1-7](#)). For subjects who discontinue during the Double-Blind Period, if either the Day 85 or Day 169 visit falls within  $\pm 14$  days of the Week 24 Post-Study Drug Efficacy Visit ([Table 5.1-4](#)), only perform immunogenicity and pharmacokinetic blood samples ([Table 5.1-7](#)) along with the Post-Study Drug Efficacy Visit.

The only exception to this requirement is when a subject withdraws consent for all study procedures including post-treatment study follow-up or loses the ability to consent freely (ie, is imprisoned or involuntarily incarcerated for the treatment of either a psychiatric or physical illness).

Subjects **MUST** discontinue investigational product (and non-investigational product at the discretion of the investigator) for any of the following reasons:

- Subject's request to stop study treatment
- Subject withdraws consent
- Any clinical adverse event (AE), laboratory abnormality or intercurrent illness which, in the opinion of the investigator, indicates that continued participation in the study is not in the best interest of the subject
- Pregnancy (see additional instruction below)
- Termination of the study by Bristol-Myers Squibb (BMS)
- Loss of ability to freely provide consent through imprisonment or involuntarily incarceration for treatment of either a psychiatric or physical (e.g., infectious disease) illness
- Use of prohibited medication
- Subjects who fail rescue therapy, as judged by the investigator, between Wk 12 and Wk 24
- Subjects who, during the course of the study, require mechanical breathing assistance (ventilator) due to myositis, ILD, or another pulmonary cause. Temporary mechanical breathing assistance during a procedure or elective surgery is permitted.
- Missed Doses
  - Missed 4 or more doses of abatacept/placebo for any reason during the first 24 weeks (Double-Blind Period)
  - Missed 3 or more consecutive doses of abatacept/placebo for any reason during the first 24 weeks (Double-Blind Period)
  - Missed 6 or more doses of abatacept for any reason between Week 24 and Week 52 (Open-Label Period)
  - Missed 5 or more consecutive doses of abatacept for any reason between Week 24 and Week 52 (Open-Label Period) or Week 76 (for subjects randomized in Japan)
- Significant non-compliance with protocol (i.e., procedures, assessments, medication, etc.). The investigator should discuss such issues with the BMS Medical Monitor.
- Participation in another clinical trial with an investigational product.

In the case of pregnancy, the investigator must immediately notify the Sponsor or designee of this event. In most cases, the study drug will be permanently discontinued in an appropriate manner. Please contact the Sponsor or designee within 24 hours of awareness of the pregnancy. If the investigator determines a possible favorable benefit/risk ratio that warrants continuation of study drug, a discussion between the investigator and the Sponsor or designee must occur.

If study drug is discontinued prior to the subject's completion of the study, the reason for the discontinuation must be documented in the subject's medical records and entered on the appropriate case report form (CRF) page.

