### **3.1.3 Open-Label Period (Week 24 - Week 52) and Open-Label Extension Period (Week 52 - Week 76) for Japan**

The 24-week Double-Blind Period is followed by a 28 week open-label abatacept treatment period (Open-Label Period, see [Table 5.1-3](#)). During this period, subjects initially randomized to receive

the combination of abatacept and standard treatment will continue this regimen. Subjects who are initially assigned to receive standard treatment alone will be switched to standard treatment plus abatacept.

There will also be a 24 weeks (168 days) open label extension for subjects randomized in Japan.

Background treatment may be adjusted (including the dose of corticosteroids and immunosuppressants) at any time during this period. Use of immune globulin (intravenous [IVIG] or subcutaneous [SCIG] is permitted during this period. Addition of any other prohibited medication ([Section 3.4.2.1](#)) is not permitted.

During this period, subjects who have clinically active or relevant interstitial lung disease (ILD) or anti-synthetase syndrome as determined by the investigator, may have to repeat pulmonary function testing and HRCT scan of the chest at Wk 52. (See [Section 5.3.6](#) and [Section 5.3.7.2](#)) and at Wk 76 for Japan.

Subjects who participate in the sub-study of MRI muscle (thigh) imaging will have an MRI performed at Wk 52. See [Section 5.8.2](#)

Subjects who discontinue treatment with abatacept during the Open-Label Period or Open Label Extension for Japan will complete the Early Termination visit for the OL (See [Table 5.1-3](#) day 365 is also the OL ET) and 2 follow-up visits during the 24 week post-treatment follow-up period, to perform safety and laboratory assessments. (See [Table 5.1-7](#)). If the subject receives treatment with an alternate source of abatacept (Post-Study Drug Program [PSDP] or Commercial), completing this post-treatment follow-up period is not required.

Treatment with other biologic therapy is not recommended for at least 70 days (~5 half-lives of abatacept follow-up period.

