### **3.1.6 Post-Treatment Follow-Up Period**

The Post-Treatment Follow-Up Period (see [Table 5.1-7](#)) will last 24 weeks (169 days). The Post-Treatment Follow-Up is required for subjects who discontinue study treatment and do not start abatacept from an alternative source. This applies to subjects who either complete or early terminate any of the study periods (DB, OL, OL-EXT, or LTE). The purpose of this Period is to perform safety and laboratory assessments.

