### **6.1.1 Serious Adverse Event Collection and Reporting**

Section 5.5.1 in the Investigator Brochure (IB) represent the Reference Safety Information to determine expectedness of serious adverse events for expedited reporting. Following the subject's written consent to participate in the study, all SAEs, whether related or not related to study drug, must be collected, including those thought to be associated with protocol-specified procedures. All SAEs must be collected that occur during the screening period through 24 weeks after discontinuation of dosing.

The investigator must report any SAE that occurs after these time periods and that is believed to be related to study drug or protocol-specified procedure.

An SAE report must be completed for any event where doubt exists regarding its seriousness.

If the investigator believes that an SAE is not related to study drug, but is potentially related to the conditions of the study (such as withdrawal of previous therapy or a complication of a study procedure), the relationship must be specified in the narrative section of the SAE Report Form.

SAEs, whether related or not related to study treatment, and Pregnancies must be reported to BMS (or designee) immediately within 24 hours of awareness of the event.

SAEs must be recorded on the SAE Report Form. The required method for SAE data reporting is through the eCRF. The paper SAE Report Form is only intended as a back-up option when the electronic data capture (EDC) system is unavailable /not functioning for transmission of the eCRF to BMS (or designee). In this case, the paper form is transmitted via email or confirmed facsimile (fax) transmission. When paper forms are used, the original paper forms are to remain on site.

Pregnancies must be recorded on a paper Pregnancy Surveillance Form and transmitted via email or confirmed facsimile (fax) transmission.

[REDACTED]

If only limited information is initially available, follow-up reports are required. (Note: Follow-up SAE reports must include the same investigator term(s) initially reported.)

If an ongoing SAE changes in its intensity or relationship to study drug or if new information becomes available, the SAE report must be updated and submitted within 24 hours to Sponsor or designee using the same procedure used for transmitting the initial SAE report.

All SAEs must be followed to resolution or stabilization.

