6 STUDY PERIODS, TREATMENT REGIMENS AND POPULATIONS FOR ANALYSES

6.1 Study Periods

There are 6 analysis periods defined for the study: the 5 study periods ((i) pre-treatment period; (ii) 24-week DB period; (iii) the OL period; (iv) the OLE period for Japan; (v) the LTE period, incorporating the OLE period for Japan) and (vi) the cumulative abatacept period. These periods will be used in the safety summaries.

The pre-treatment period: covers the time period prior to the first dose date/time of study medication.

The 24-week Double-Blind period: starts at the first dose date/time of double-blind study medication and lasts until the last dose date of the double-blind period + 56 days if subjects discontinue the study during double-blind period, or until the first dose in the open-label period.

Since the dosing information for the Open-Label period, the Open-Label Extension period and the Long-Term Extension period is recorded on the same CRF page, it is not possible to derive the first/last dose for the different periods based on that CRF page. This is why start and end visit dates from other CRF pages will be used to distinguish between these 3 periods. Start and end visit dates are recorded for most periods, except the start of the OLE period for Japan subjects, this will be

assumed to be the end of the OL period. These dates will be used for deciding which dose belongs to which period.

The Open-Label period: starts at the first dose of the open-label period and lasts until the last dose date of open-label period + 56 if subjects discontinue the study during open-label period (or if subjects are from U.S. and Czech Republic sites), or until the first dose in the open-label extension period for subjects from Japanese sites, or the first dose in the long-term extension period for subjects from other sites.

The Open-Label Extension period (Japan subjects only): starts at the first dose of the open-label extension period (determined as the open-label period end visit date from the CRF) and lasts until the last dose date of open-label extension period + 56 if subjects discontinue the study during open-label extension period, or until the first dose in the long-term extension period.

The Long-Term Extension period (all subjects except for U.S. or Czech subjects): starts at the first dose of the long-term extension period and last until the last dose date of long-term extension period + 56.

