11.5.1.1 Open-Label Period Exposure

The extent of exposure for the open-label period will be calculated and presented in days as follows:

- For subjects who discontinued during the open-label period or did not enter the open-label extension period or the long-term extension period within 56 days of the last injection in the open-label period:
- Exposure in days = (date of last injection in the open-label period - date of first open-label injection + 1) + 56.

For subjects who enter open-label extension or long-term extension period within 56 days of the last injection in the open-label period:

- Exposure in days = (date of first injection in the open-label extension or long-term extension period - date of first open-label injection).

The offset of 56 days is the length of 2 regular dosing cycles and represents approximately 4 times the half-life of Abatacept in humans.

Summaries of exposure to study drug will show the distribution of the number of injections and days on drug, together with the means, standard deviations, medians, minima and maxima, by treatment group.

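### Protocol 3.5 and 3.1.6 disagree on post-treatment visits for subjects who move to other abatacept, and the SAP's last dose + 56 days makes no provision for these subjects

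*Protocol*

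**What the plan says.** Protocol 3.5 states the rule without limit of period, counting days from the last dose: "All subjects who discontinue study drug at any time throughout the study, require visits to assess safety and immunogenicity at Day 85 and Day 169". It then names a single exception, in two parts. The first reads: "The only exception to this requirement is when a subject withdraws consent for all study procedures including post-treatment study follow-up". The second is that consent can no longer be given freely.

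Protocol 3.1.6 says otherwise: "The Post-Treatment Follow-Up is required for subjects who discontinue study treatment and do not start abatacept from an alternative source". It applies this to completers and early terminators of every period. Sections 3.1.3 (open-label period and Japan extension) and 3.1.4 (long-term extension) say that with Post-Study Drug Program or commercial abatacept "completing this post-treatment follow-up period is not required". The title of Table 5.1-7 carries the same exemption. Section 3.1.2, for the Double-Blind Period, mentions commercial abatacept only. SAP 2.1 repeats the exemption.

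Serious events are handled separately in Protocol 6.1.1: "All SAEs must be collected that occur during the screening period through 24 weeks after discontinuation of dosing".

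In SAP 6.1 the double-blind safety period "lasts until the last dose date of the double-blind period + 56 days if subjects discontinue the study during double-blind period", or else ends at the first open-label dose. SAP 11.5.1.1 gives, for a subject who does not go on to an extension, "Exposure in days = (date of last injection in the open-label period - date of first open-label injection + 1) + 56". SAP 7.4.1.1, 11.5.1.2, 11.5.1.3 and 11.5.1.4 add the same 56 days. None of them mentions abatacept from another source. SAP 11.7 uses these exposures as the denominator of rates per 100 person-years.

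**The concern.** A site that follows 3.5 schedules two safety visits for a subject who moves to other abatacept; a site that follows 3.1.6 schedules none. Safety follow-up would then depend on which section a site happened to read.

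Two consequences follow in the SAP. In the Double-Blind Period, a fixed 56-day tail can take in time on commercial abatacept and assign it to the placebo group, which blurs the only randomized safety comparison. In the open-label and long-term periods, the tail adds person-time for exempt subjects, most of it after their last scheduled study visit. If events in that time go unrecorded, the denominator grows and the numerator does not.

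**Working it through.** **1. The plan's own figure.** Protocol 3.3.1 equates 5 half-lives with 70 days, so one half-life is 70 / 5 = 14 days. Four half-lives are 4 × 14 = 56 days, which matches the basis given in SAP 7.4.1.1.

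**2. Visits required of a subject who stops and takes abatacept from another source.**
- Protocol 3.5: two.
- Protocol 3.1.3, 3.1.4, 3.1.6 and Table 5.1-7: none.
- Protocol 3.1.2: none if the source is commercial; it does not mention the Post-Study Drug Program.

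Section 3.5 cites Table 5.1-7 as its schedule, so it conflicts with the title of its own table. Section 3.6 also drops subjects lost to follow-up, who are not in 3.5's exception either.

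**3. Double-Blind Period.** If a placebo subject starts commercial abatacept *s* days after the last dose, with *s* below 56, then 56 − *s* days on abatacept fall in the placebo window. For illustration, *s* = 14 gives 42 of 56 days. The As-Treated definition (SAP 6.3) regroups a subject only if the other treatment was received for the whole Double-Blind Period, so it does not correct this.

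**4. Open-label completer with no extension (for example U.S. or Czech).** The first open-label dose is Day 169 and the last visit Day 365 (Table 5.1-3). The last dose is in Week 51 (Protocol 4.5.1), taken as 51 × 7 + 1 = Day 358.
- Exposure: 358 − 169 + 1 + 56 = 246 days.
- Days after the last scheduled visit: (358 + 56) − 365 = 49, which is 49 / 56 = 87.5% of the added days.
- Share of exposure: 49 / 246 = 19.9%.

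**5. Long-term extension completer.** The last dose is Day 1086 (Protocol 4.5.1) and the last visit Day 1093 (Table 5.1-6).
- Exposure by SAP 11.5.1.3: 1086 − 1 + 56 = 1141 days.
- Days after the last scheduled visit: (1086 + 56) − 1093 = 49.
- Share of exposure: 49 / 1141 = 4.3%.

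**6. Cumulative abatacept exposure.**
- Abatacept arm, ending at Week 52: 358 − 1 + 1 + 56 = 414 days, and 49 / 414 = 11.8%.
- Through the long-term extension outside Japan, last dose on study day 364 + 1086 = 1450: 49 / 1506 = 3.3% (abatacept arm) and 49 / 1338 = 3.7% (placebo arm, abatacept from Day 169).

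**7. From days to rates.** If event risk is constant and a fraction *c* of events in the 49 days is recorded, the rate for such a subject is lowered by share × (1 − *c*). With *c* = 0 this is the full 19.9% or 4.3%. With *c* = 0.5 it is 10.0% or 2.1%. With *c* = 1 it is zero.

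**8. Comparison with followed subjects.** The first follow-up visit is Day 85 ± 14, that is 71 to 99 days after the last dose. Followed completers also have no follow-up visit inside the 56 days. What exempt subjects lose is the later visit that would ask about that time.

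**9. Double-blind discontinuers.** They keep the Day 169 efficacy visit, which includes adverse event monitoring (Protocol 3.1.2, Table 5.1-4). At its target day it looks back over all 56 days if the last dose was by Day 113 (169 − 113 = 56), over 28 days for Day 141 and over 7 days for Day 162.

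**The case against.** The strongest reply on the visit rule is that the intent is easy to guess: 3.5 points to a table whose title carries the exemption, and most other passages agree with that title. This stands as a comment on intent. The wording of 3.5, with its single exception, still contradicts the other sections.

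On the rates, a reader might infer that open-label and long-term rates are too low, or that a fifth of open-label person-time is unobserved. The documents do not support that. Serious events must be collected for 24 weeks whether or not visits occur, events may be reported spontaneously (Protocol 6), and supply through the Post-Study Drug Program may be an extension or rollover study (Protocol 3.2) whose contacts are not described. The shares above assume that nothing is captured and belong to one kind of subject. A trial-level figure would need the proportion of exempt subjects, for which the documents give no basis.

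A reader might also infer that exempt subjects are selectively those doing well. Section 3.2 ties benefit to the Post-Study Drug Program only and says nothing of the kind about commercial abatacept.

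On the double-blind point, no frequency is given, and Week 24 events are summarized as percentages and risk differences rather than person-time rates. That limits the size. It does not settle which group the events belong to, and the retained Day 169 visit may collect such events and place them under placebo.

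Finally, SAP 11.7 already runs the numerator to 56 days after the last dose and the denominator includes the same 56 days, so their end dates already correspond. Replacing this with a cut at last study contact would be a poor remedy. If a serious event report counts as contact, person-time lengthens only for subjects with events; if it does not, serious events that 6.1.1 requires are dropped.

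**Conclusion.** The point holds in three parts.

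- Protocol 3.5 contradicts 3.1.2, 3.1.3, 3.1.4, 3.1.6 and the title of Table 5.1-7 on who has post-treatment visits. The documents do not say how the 24-week serious event collection is met for subjects without those visits.
- The double-blind window can assign on-abatacept events to placebo when a subject starts commercial abatacept within 56 days. The number of such subjects is not stated.
- In the later periods, 49 of the 56 added days follow the last scheduled visit for an exempt completer. Any downward bias is at most 19.9% of an open-label completer's exposure and 4.3% of a long-term extension completer's. It concerns mainly nonserious events and is reached only if none is captured in those days.

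The figures assume dosing and visits on the protocol's target days. The primary efficacy endpoint is untouched. The correction is worth making because it is cheap and concerns safety follow-up.

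**What to change.** **Protocol.** Reconcile 3.5 with 3.1.2–3.1.4, 3.1.6 and Table 5.1-7 so that one rule says who has post-treatment visits. Which rule is for the sponsor to decide. State in the same place how the collection required by 6.1.1 is met for any subject without those visits.

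**SAP 6.1 and 7.4.1.1.** End the double-blind adverse event window and exposure, in both arms, at the earlier of last dose + 56 days and first dose of alternate-source abatacept. SAP 6.1 already ends that window at the first open-label dose, so this extends an existing rule. Events after the cut remain in the comprehensive listing described with the Week 24 adverse event summaries.

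**SAP 11.5.1 and 11.7.** Keep last dose + 56 days as the main analysis for the later periods. Add a sensitivity rate in which exempt subjects' events and person-time both stop at the last scheduled visit, and report how many subjects are exempt.

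**Cost.** A protocol clarification, a few lines of SAP text, slightly less person-time and one additional table. The start date of alternate-source abatacept must be in the database.
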